Outcome measures in this study were created for this evaluation and are not based on already-validated scales. Using the local evaluation baseline survey, we will generate a correlation matrix between items in a given construct to ensure that theoretically related items are also empirically related in our data set. Items that are not strongly correlated with other items in a construct will be removed as necessary. Factor analysis will be used to ensure that all construct items hang together (using an alpha of 0.60 or higher as the threshold). We will then create a composite measure by taking an average of the scores on each non-missing item in the construct. For composite measures, a change score will be calculated between a participant's pre-program composite score and six-month-post-enrollment follow-up composite score. If construct items do not meet the 0.60 threshold, that outcome will be removed. An alpha value of 0.60 is the minimally acceptable value that will be used for scale construction.

We will create a composite score by taking the average of multiple individual items. For these composite measures, our plan is to use 20% as a threshold for allowable missing items. This plan is contingent on the final distribution of missing data in our dataset. With a 20% threshold, if a respondent is missing more than 1 item used for creating the employment construct or more than 2 items for creating the financial construct, the respondent will be assigned a missing value for that construct. We will not impute truly missing values for outcomes. To create a construct score, the average will be divided by the number of non-missing values in the construct.

Table 1. Description of outcome measures used to answer impact analysis primary research questions

Research question #	Outcome name	Description of the outcome measure and its properties	Source of the measure	Timing of measure
1	Employment Attitudes	
The outcome measure is a scale (value range of 1=strongly disagree to 5=strongly agree) calculated as the average of eight survey items related to employment attitudes.
 
Sample item: I have the skills I need to get a decent job.
	Local evaluation follow-up-survey	Six months after program enrollment

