2	Financial Attitudes	
The outcome measure is a scale (value range of 1=strongly disagree to 5=strongly agree) calculated as the average of seven survey items related to financial attitudes.
 
Sample item: I am overwhelmed when I think about my financial situation.
	Local evaluation follow-up-survey	Six months after program enrollment

Table 2. Description of outcome measures used to answer impact analysis secondary research questions

Research question #	Outcome name	Description of the outcome measure and its properties	Source of the measure	Timing of measure
1	Relationship Behaviors	
The outcome measure is a scale (value range 1=never to 4=often) calculated as the average of seven survey items related to the frequency of healthy intimate partner/spouse relationship behaviors.
 
Sample item: When my partner/spouse and I had a serious disagreement, we discussed our disagreements respectfully.
 
Note: skip logic is built into the survey. If a participant is not currently in a committed relationship, he or she will be asked to move to the next section of the survey.
	Local evaluation follow-up survey	Six months after program enrollment
2	Relationship Attitudes	
The outcome measure is a scale (value range of 1=strongly disagree to 5=strongly agree) calculated as the average of eight survey items related to intimate partner/spouse attitudes and expectations
 
Sample item:
	Local evaluation post-survey	After program completion

Research question #	Outcome name	Description of the outcome measure and its properties	Source of the measure	Timing of measure
		
My partner and I can handle any conflicts that come up in our relationship.
 
Note: skip logic was built into the survey in Oct 2023. If a participant is not currently in a committed relationship, he or she will be asked to move to the next section of the survey.
		

B. Description of the focal population and the intervention and counterfactual conditions

This section provides a brief description of the focal populations, the intervention being evaluated, and the services that are intended as the comparison to the intervention, including any service-as-usual resources available. In addition, it includes a description of the services actually received by the intervention and comparison groups.

1. Focal population(s)

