Each of the outcomes for the primary research questions for this study are constructed averages using multiple, related survey items. Sufficiently high item nonresponse among items used to construct outcome measures will lead to sample attrition for that outcome. The evaluation team plans to use an 80% threshold as the cutoff for constructed measures; respondents who answer less than 80% of survey items associated with a constructed measure will be dropped from the analysis for that outcome. The constructed average for each participant who has answered at least 80% of associated survey items will be calculated by dividing the sum of their survey answers by the number of items they answered. For example, if a participant answers 8 out of 10 survey items associated with a construct, their average for that outcome measure will be the sum of their 8 answers divided by 8. The evaluation team does not plan to use imputation for multi-item constructed outcomes with 20 percent or fewer missing items. A sensitivity analysis will be conducted to see if and how results would change with a 70% threshold cutoff instead of an 80% cutoff.

2. Attrition and analytic sample

The analytic sample for each outcome construct identified in Table 2 will consist of study participants who have a non-missing value at baseline and follow-up time points for that construct (complete case). The size of the analytic sample may vary by outcome measure based on the prevalence of item non-response missing data at the baseline and follow-up surveys for the items used to create those composite measures. For attitudinal outcomes related to economic stability, and finances, all respondents with complete case data will be included in the analytic sample. For relationship behavior outcomes, participants will be included in the analytic sample if they report being in a committed relationship at the time the survey was administered (i.e., do not choose 'no' for the skip logic question 'Are you currently in a committed romantic relationship?'). Because this skip logic was added to the local evaluation surveys belatedly (in October 2023), this condition will only apply to those respondents who took a survey with this skip logic. For those respondents who took a survey before this relationship skip logic was added, all participants who have complete case data will be included in the analytic sample in response to the secondary research question.

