All outcome measures for this study are constructed averages calculated using a number of theoretically and empirically related survey items. As mentioned in the previous section, a respondent who answers some but not all survey items in a given outcome construct will have their outcome value assigned as missing if they do not respond to at least 80% of the items in the construct. We will not impute missing baseline or outcome data for our analyses. Based on the recommendation from ACF, we will use the cautious attrition threshold from the What Works Clearinghouse (WWC) to assess whether attrition can be considered high or low.

Assessment of baseline equivalence

Per the WWC's standards, we will use effect sizes (i.e., standardized mean differences), to examine the baseline equivalence between the study groups. Effect size is defined as the difference between the intervention group mean and the comparison group mean, divided by the pooled standard deviation. We will calculate the effect size for demographic characteristics (such as gender, age, and race/ethnicity, as reported on the nFORM Applicant Characteristics Survey) and each baseline outcome of interest depending on the type of variable: Hedge's g , for continuous variables; and Cox's index, for dichotomous variables. We can determine baseline equivalence by comparing each outcome's effect size using the WWC standard, which suggests that if the corresponding effect size is 0.05 or less in absolute value, it is considered "small," and we can conclude that it satisfies baseline equivalence without statistical adjustment. However, if the effect size falls between 0.05 and 0.25, it is considered "moderate," and it will require a statistical adjustment to meet baseline equivalence (we will use statistical adjustments such as regression adjustments or matching/weighting). Lastly, in the case that the effect size is greater than 0.25, it will be considered "large", which shows that the differences at baseline are too large to meet WWC standards, even with statistical adjustments. In that case, we will apply appropriate caveats to any interpretation of the results.

Condition crossover

At the primary RCT enrollment site, Franklin CBCF, condition crossover is not possible due to restrictions put in place when designing the implementation of the two delivery formats. If a participant who was

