Analyses will be conducted using the R Studio statistical software package. The basic model for this impact evaluation will include a dummy variable for intervention group assignment, equal to 1 if a participant was randomly assigned to receive the curriculum on-demand via tablet, and a participant's score at baseline as the main predictors of each outcome measure at follow-up. To enhance the precision of the impact estimates, we plan to include several other covariates in our models. For all outcome analyses, we will control for participant age, gender, and race, as well as the timing of a participant's follow-up survey (number of days between program enrollment and follow-up survey completion). We will also consider including a facility indicator to denote which site the participant received services at. Additionally, we will include any demographic variables that were shown to be significantly different between study groups during baseline equivalency analysis. For the healthy relationship attitudes outcome, we also plan to include relationship status at baseline as a covariate. This will only be available if a participant reports being in a relationship at baseline and at follow-up.

Table 6. Covariates included in impact analyses

Covariate	Description of the covariate
Age	Age (in years) as of the baseline data collection, as reported on the ACS
Gender	Self-reported gender identification as of the baseline data collection, as reported on the ACS
Race	Self-reported racial identification as of the baseline data collection, as reported on the ACS

Covariate	Description of the covariate
Timing of follow-up survey	Number of days between program enrollment date and date of follow-up survey completion to control for variation in survey timing
Relationship status (relationship attitude and behavior outcomes only)	Relationship status (1 = in a committed relationship, 0 = not in a committed relationship) as of the baseline data collection, as reported on the ACS

4. Sensitivity analyses for primary research questions

We plan to conduct several sensitivity analyses to test the robustness of our results. First, and as mentioned earlier in the plan, we will conduct a sensitivity analysis to see if and how our outcome construct measures change if we use 70% as a threshold for non-missing items instead of 80% as a threshold.

[figure not shown]

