Partner relationship attitudes/expectations 8 items	Added skip logic allows participants to only respond to these items if they indicate that they are currently in a committed relationship.	No	Yes
Partner relationship behaviors 2 sets of questions: 7 items 11 items			Yes (only the first set of items containing 7 items)
Finance attitudes 7 items	Shown to all participants	Yes	No
Finance behaviors 4 items		No	No
Employment attitudes 8 items	Shown to all participants	Yes	No
Employment behaviors 5 items	Added skip logic allows participants to only respond to these items if they indicate that they are currently employed.	No	No
Parenting attitudes 8 items	Added skip logic allows participants to only respond to these items if they indicate that they have at least one child.		
Parenting behaviors Based on child's age 11 items (>age 6 & = < age 12), 9 items (< age 1 & = <6), 11 items (for child = <1)		No	No
Co-Parenting attitudes 5 items			

References

Bandura, A (1977). Self-efficacy: Toward a Unifying Theory of Behavioral Change. *Psychological Review*. 84 (2), 191–215.

Chou, S., & Liu, C. (2005). Learning effectiveness in a web-based virtual learning environment: A learner-control perspective. *Journal of Computer Assisted Learning*, 21(1), 65 - 76.

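### The missing-item limit for the primary financial scale (2 of 7) breaks the plan's own 20%/80% rule, and under that limit the 70% sensitivity analysis changes nothing for financial attitudes

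*Combined protocol and SAP*

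**What the plan says.** Section A.3 sets the allowable share of missing items at 20% and turns it into counts. The score is set to missing for a respondent "missing more than 1 item used for creating the employment construct or more than 2 items for creating the financial construct". So 1 missing employment item and 2 missing financial items are tolerated.

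The financial scale has seven items in both places where its length is given. Table 1 describes it as "calculated as the average of seven survey items related to financial attitudes", and Figure A.4 lists "Finance attitudes 7 items". The employment scale has eight.

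The analysis section states the rule as a percentage. Section D.1 (Constructed outcome measures): "respondents who answer less than 80% of survey items associated with a constructed measure will be dropped from the analysis for that outcome". Section D.2: a partial respondent "will have their outcome value assigned as missing if they do not respond to at least 80% of the items in the construct". Sections D.1 and D.4 add a sensitivity analysis that uses "70% as a threshold for non-missing items instead of 80% as a threshold".

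Scale length is not final. Section A.3 also says: "Items that are not strongly correlated with other items in a construct will be removed as necessary".

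**The concern.** The count of 2 is offered as the result of a 20% limit, but 2 of 7 is well above 20%. A respondent with five of seven financial items answered is analysed under A.3 and excluded under D.1 and D.2. Two analysts could each follow the plan and obtain different samples for a primary outcome.

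The rule decides who is analysed. The analysis is complete case, needs a score at both baseline and follow-up, and does not impute missing baseline or outcome data. The choice between the two rules could also be made after the data are seen.

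The planned check on the rule is affected too. If the looser count is already used in the primary analysis, relaxing the cutoff to 70% may admit nobody new.

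**Working it through.** **Inputs.** Financial items k = 7 (Table 1, Figure A.4). Employment items k = 8 (Table 1, Figure A.4). Primary cutoff 80% answered (D.1, D.2), equivalent to 20% missing (A.3). Sensitivity cutoff 70% (D.1, D.4). Target analytic sample 768 (C.1).

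**Step 1: try to reproduce the stated counts.** The largest allowed number missing, m, satisfies (k − m)/k ≥ 0.80.

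- Employment: 0.8 × 8 = 6.4, so 7 must be answered and m = 1. This matches A.3.
- Financial: 0.8 × 7 = 5.6, so 6 must be answered and m = 1. A.3 says 2. With 2 missing, 5/7 = 71.4% are answered and 28.6% are missing.

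Rounding does not explain it. For 20% of 8 = 1.6 and 20% of 7 = 1.4, the pair (employment, financial) is (1, 1) rounding down, (2, 1) rounding to nearest and (2, 2) rounding up. No single rule gives the stated (1, 2), which puts the looser limit on the shorter scale. A limit of 2 at 20% first arises with 10 items, the length used in D.1's generic example ("if a participant answers 8 out of 10 survey items associated with a construct").

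**Step 2: compare with the 70% cutoff, and allow for item removal.**

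| Items retained | Needed at 80% | Max missing | Needed at 70% | Max missing | Answered if 2 missing |
|---|---|---|---|---|---|
| 8 | 7 (6.4) | 1 | 6 (5.6) | 2 | 75.0% |
| 7 | 6 (5.6) | 1 | 5 (4.9) | 2 | 71.4% |
| 6 | 5 (4.8) | 1 | 5 (4.2) | 1 | 66.7% |
| 5 | 4 (4.0) | 1 | 4 (3.5) | 1 | 60.0% |

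With seven items, the A.3 count (2 missing) and the 70% cutoff (2 missing) are the same inclusion rule. With the correct limit of 1, the 70% analysis adds respondents who miss exactly 2 items. For employment it moves the limit from 1 to 2 in any case.

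Removing items does not rescue the count. With six items, 2 missing fails even the 70% cutoff, so a fixed limit of 2 would make the primary rule looser than its relaxed check. With six or five items, the 80% and 70% rules coincide.

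**Step 3: size.** The affected respondents have at most 2 financial items missing at each wave and exactly 2 at one wave or both. The documents give no item non-response for these items. Assume that items are skipped independently with probability q, and that the two waves are independent. The affected share is then P(M ≤ 2)² − P(M ≤ 1)², with M binomial (7, q).

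| Assumed q | P(M ≤ 2) | P(M ≤ 1) | Affected share | Of 768 |
|---|---|---|---|---|
| 1% | 0.99997 | 0.99797 | 0.40% | 3.1 |
| 2% | 0.99974 | 0.99214 | 1.51% | 11.6 |
| 5% | 0.99624 | 0.95562 | 7.93% | 60.9 |

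**The case against.** The best defence is that the percentage rule plainly governs. It appears in A.3, D.1, D.2 and D.4, while the count of 2 appears once, as an illustration of it. An analyst working from section D would code 80%, and the 70% check would then work as intended. This bears on how likely the error is to reach the analysis. It does not make the count right, and A.3 is where the primary outcomes are defined.

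A second point is that A.3 makes the threshold depend on the missingness eventually observed, so correcting the count does not by itself fix the sample in advance. That is true, and the sentence needs attention too. But it permits a later change of threshold; it does not explain a count presented as following from 20%.

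Third, the 70% analysis is empty only if the A.3 count is used, and D.4 also plans a mean-imputation check on missing scale items. Both statements are correct, so the consequence is conditional.

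Finally, the size is hypothetical. Skipped items may cluster within respondents, which could move the figures either way, and 768 is a target. At the July 2024 data pull, Figure A.3 shows 64 + 52 = 116 completed follow-ups. The same shares of 116 are about 0.5, 1.8 and 9 people. No effect on the treatment estimate has been shown. The case therefore rests on the contradiction, not on a large expected effect.

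**Conclusion.** The concern holds. With seven items, the 20%/80% rule allows 1 missing financial item, not 2, and no rounding convention or item removal reconciles the two. The 70% analysis is uninformative for financial attitudes if the A.3 count is used, and informative if D.1 and D.2 are followed. Employment attitudes is unaffected.

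The arithmetic on the limits needs no assumption. The number of respondents affected cannot be computed from the documents; the illustrative range rests on assumed, independent item non-response and is probably small if few items are skipped. The point should be corrected before analysis because it decides who is analysed for one of two primary outcomes.

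**What to change.** In section A.3, replace the two counts with wording such as:

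> A respondent must answer at least 80% of the retained items. With all items retained, this allows at most 1 missing item on both the 8-item employment scale and the 7-item financial scale. The 70% sensitivity analysis allows at most 2 on each. If items are removed, both limits are recomputed, and we will state where they coincide.

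The last clause matters because the 70% analysis adds nothing once a scale falls to six or five items. To settle the rule in advance, A.3 should also say that the 80% cutoff defines the primary analysis whatever missingness is observed, with other cutoffs reported as sensitivity analyses.

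Two minor edits can be made at the same time; the finding does not depend on them. Delete the A.3 sentence that divides an average again by the count of answered items, since A.3, D.1 and D.4 elsewhere define the mean correctly. State item direction and any reverse-scoring before the correlation and alpha steps, because the one financial item shown in Table 1 is negatively worded.

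The cost is wording only. Compared with the A.3 count, the primary financial analysis may lose a few respondents (about 3 to 12 of 768 at an assumed 1–2% item non-response, more if it is higher). With all seven items retained, the 70% analysis would bring them back.

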Participants are considered active in the study for six months, from the time that they enroll in the program to the completion of the six-month post-enrollment follow-up survey.

The target analytic sample size for the impact study is 768 participants, with study groups being equal in size, for a target of 384 in-person participants and 384 on-demand participants.

Participant eligibility criteria. Individuals are eligible to participate in the program if they are incarcerated adults aged 18 years or older and within nine months of release from prison. All program enrollees who are receiving services at a site that has been authorized by the Ohio Department of Rehabilitation and Corrections (ODRC) to use tablets (and so can offer both delivery formats) for this program are eligible for the impact evaluation after giving informed consent to be randomly assigned to a study group. Approvals are for a specific tablet that the state of Ohio has granted a contract to provide technology services and devices into prisons across the state. Each warden (head of the specific institution) must approve the program delivered via tablet in their specific institution. This design allows for more equal opportunity for participants to be assigned to either delivery format. It also puts less burden on The RIDGE Project to meet enrollment numbers at numerous locations in order to get a sufficient sample to randomize. Program participants who have other commitments that prevent them from being able to participate in the in-person workshops are not eligible for random assignment; these participants are still offered TYRO Couples programming, but they are not part of the impact study sample. This within-facility design offers The RIDGE Project the opportunity to serve those in need without ever having to deny eligible applicants. In instances where unexpected situations arise, such as technological issues with the tablets, participants can opt out of the treatment group and receive in person services if it is more convenient or preferable to them. This would remove the participant from the study, but still allow the participant to continue with the TYRO curriculum. Having sites offer both delivery formats is invaluable for program delivery.

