To increase follow-up response rates and with the approval of OFA, alternative follow-up data collection procedures were developed by the RIDGE and evaluation teams for one service site that enrolls most of the impact study participants at about 78%, Franklin CBCF. Many impact study participants from the Franklin CBCF service site go on to participate in a Department of Labor initiative immediately following their release from prison. As part of this initiative, participants are bussed from the Franklin CBCF to an American Jobs Center. TYRO Couples RCT participants who are part of this initiative are invited to complete a paper follow-up survey on the Thursday prior to the bus taking participants to the American Jobs Center the following Monday morning. Eligible participants who completed the survey will be handed a physical \$50 gift card upon boarding the bus. This follows guidelines of prisons where no monetary incentives can be administered on the premises. To be eligible for the follow-up survey, participants must have a signed consent form on file and have taken either the nFORM entrance survey or the local evaluation baseline survey. Evaluation staff will coordinate with program staff to ensure only those who are eligible for the follow-up survey are offered it. Paper surveys will be sealed in an envelope where they are given to a team member certified in protecting human research participants to enter the surveys into Qualtrics. Paper surveys are to be kept in locked storage at RIDGE offices and will be stored for a minimum of three years before being destroyed in accordance with IRB guidelines. This process is set to begin in May 2024.

Table 5. Key features of the data collection

Study group	Data source	Timing of data collection	Mode of data collection	Party responsible for data collection	Start and end date of data collection
Intervention (on-demand)	Survey Wave 1 (nFORM baseline and local evaluation baseline surveys)	Immediately following informed consent and randomization during orientation (within 1-2 weeks of enrollment)	In-person paper survey	RIDGE Staff	April 11, 2023 – November 30, 2024
	Survey Wave 2 (nFORM exit and local evaluation post-surveys)	Six weeks after program enrollment	In-person paper survey	RIDGE Staff	May 23, 2023 (or February 2023 for pilot cohort) – January 11, 2025

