	Survey Wave 3 (Local evaluation follow-up survey)	Six months after program enrollment; Between three to six months after program enrollment at Franklin CBCF	Online via a QR code or email link; over the phone; in person paper survey if in the eligible Franklin CBCF group	MER Staff or RIDGE facilitator if in the eligible Franklin CBCF group	October 2023 – May 31, 2025 for all locations aside from Franklin CBCF; For Franklin CBCF- May 2024- May 31, 2025

Study group	Data source	Timing of data collection	Mode of data collection	Party responsible for data collection	Start and end date of data collection
Counterfactual (in-person)	Survey Wave 1 (nFORM baseline and local evaluation baseline surveys)	Immediately following informed consent and randomization during orientation	In-person paper survey	RIDGE Staff	April 11, 2023 (or January 2023 for pilot cohort) - November 30, 2024
	Survey Wave 2 (nFORM exit and local evaluation post-surveys)	Six weeks after program enrollment, immediately following the last primary workshop session	In-person paper survey	RIDGE Staff	May 23, 2023 (or February 2023 for pilot cohort) – January 11, 2025
	Survey Wave 3 (Local evaluation follow-up survey)	Six months after program enrollment; Between three to six months after program enrollment at Franklin CBCF	Online via a QR code or email link; over the phone; in person paper survey if in the eligible Franklin CBCF group	MER Staff or RIDGE facilitator if in the eligible Franklin CBCF group	October 2023 – May 31, 2025; For Franklin CBCF- May 2024- May 31, 2025

3. CONSORT diagram

The CONSORT diagram for this impact study (where random assignment occurs after consent) can be found in the appendix to this plan. The data used to complete the CONSORT diagram were pulled on July 22, 2024.

D. Analysis

This section describes the plans for defining the analytic sample, assessing baseline equivalence, cleaning data, handling missing data, and addressing potential crossover and contamination. It also describes the analytic models for estimating program impacts and planned sensitivity analyses.

1. Data preparation

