Next, we will conduct an analysis to see how outcome construct measures change if we use mean imputation to replace missing items in the multi-item scales used to create our outcome variables. This is the mean based on observed values from the rest of the sample for that item. The current plan is not to use any imputation for outcome measures, including constructed outcomes from multiple survey items, and instead to make the denominator for the calculation of the average score be equal to the number of non-missing items in that construct.

Finally, we plan to conduct a sensitivity analysis regarding the timing of the follow-up survey. Given changes in follow-up data collection protocol at Franklin CBCF, we anticipate that some respondents will have taken their paper follow-up survey earlier than intended. The sensitivity analysis will repeat our analyses using only people who completed their follow-up survey within the intended data collection window (5-7 months post-enrollment).

5. Analyses addressing secondary research questions

The analytic approach for answering the secondary research question about partner relationship behaviors will be the same as the approach taken for the primary research questions.

Figure A.3. CONSORT diagram for individual clients, for studies in which consent occurred before assignment

Eligible for 6-month post-enrollment follow-up (n = 206)

To be eligible, a participant must have provided consent and taken either the nFORM baseline or local evaluation baseline survey

Completed follow-up (n = 64)

Data collection: July 1, 2023-July 22, 2024

Reasons for non-completes (n = 1) (that can be accounted for)

Consent revoked (n = ___), declined survey (n = ___), deceased (n = ___), dropped out (n = 7), moved (n = ___), incarcerated (n = 1)

Eligible for 6-month post-enrollment follow-up (n = 190)

To be eligible, a participant must have provided consent and taken either the nFORM baseline or local evaluation baseline survey

Completed follow-up (n = 52)

Data collection: July 1, 2023-July 22, 2024

Reasons for non-completes (n = 1) (that can be accounted for)

Consent revoked (n = ___), declined survey (n = ___), deceased (n = ___), dropped out (n = 4), moved (n = ___), incarcerated (n = 1)

Figure A.4. Survey items linked to research questions

Measure	Item Response	Are these items linked to a primary research question?	Are these items linked to a secondary research question?
Partner relationship beliefs 8 items			No

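### The target analytic sample of 768 is very unlikely to be reached on the plan's own counts and dates, and no projected sample or detectable effect stands beside it

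*Combined protocol and SAP*

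**What the plan says.** Section C.1 (participant numbers, under recruitment and enrolment targets) gives the only sample size in the plan: "The target analytic sample size for the impact study is 768 participants, with study groups being equal in size", that is, 384 per arm. It is a target for the analytic sample, not for enrolment. Section D.1 (Missing data) excludes people who do not return the follow-up survey. Section D.2 requires a usable construct score at both baseline and follow-up, and rules out imputing either.

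Figure A.3 gives the position part-way through. One box reads "Eligible for 6-month post-enrollment follow-up (n = 206" with "Completed follow-up (n = 64"; the other reads "Eligible for 6-month post-enrollment follow-up (n = 190" with "Completed follow-up (n = 52". The eligibility note is: "To be eligible, a participant must have provided consent and taken either the nFORM baseline or local evaluation baseline survey". Section C.3 dates the counts: "The data used to complete the CONSORT diagram were pulled on July 22, 2024". The plan itself is dated 22 August 2024.

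Table 5 gives the baseline survey period as "April 11, 2023 – November 30, 2024", with a pilot cohort from January 2023. Follow-up collection ends on 31 May 2025. Under Section C.2, active tracking stops seven months after enrolment. The same section introduces an on-site paper follow-up from May 2024 at Franklin CBCF, which enrols about 78% of participants. Section C.1 allows more facilities if enrolment falls short, but does not anticipate adding any.

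**The concern.** The target and the interim counts sit in the same document, and nothing connects them. With 116 completers in hand and about four months of enrolment left, 768 looks out of reach. No basis, expected sample or detectable effect accompanies it.

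What is at stake is how the primary result is read. Precision depends on the number analysed. If that is a third of the target, the smallest effect the study can reliably detect is well above the one that 768 implies. A null result judged against 768 would then be given more weight than the data can bear.

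**Working it through.** **The plan's own figure.** 384 + 384 = 768, so the sum is right. Its basis cannot be reproduced, because no significance level, power, effect size or attrition allowance is given. As an assumption only, 80% power at two-sided 5% needs 393 per arm (786) for 0.20 SD, which is close to 768.

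**Counts (Figure A.3).** Eligible: 206 + 190 = 396. Completed: 64 + 52 = 116. Completion: 116/396 = 29.3% (64/206 = 31.1% and 52/190 = 27.4%). Non-completers: 396 − 116 = 280.

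**Without any pace assumption.**
- Completers still needed: 768 − 116 = 652.
- If all 280 non-completers responded, 652 − 280 = 372 would still have to come from people outside the 396.
- At 29.3%, 768 completers need 768/0.293, about 2,620 eligible participants, or 6.6 times 396.
- From 22 July to 30 November 2024 is 131 days.

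**With an assumed constant pace.** Take the 396 as those at least c months past enrolment on 22 July 2024. Then:

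total enrolled = 396 × (days from start to 30 November 2024) / (days from start to the cut-off date)

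The numerator is 699 days from 1 January 2023 (pilot; day of month assumed) and 599 days from 11 April 2023. Still to come = total − 396. Completers are:
- at observed response: total × 0.293
- at an assumed 90% future Franklin response, 29.3% elsewhere: 116 + still to come × (0.78 × 0.90 + 0.22 × 0.293) = 116 + still to come × 0.766
- if everyone still to come responds: 116 + still to come

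Each cell shows the January start, then the April start.

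| c (months) | Days to cut-off | Total enrolled | Still to come | Completers at 29.3% | Franklin at 90% | All to come respond |
|---|---|---|---|---|---|---|
| 5 | 417 / 317 | 664 / 748 | 268 / 352 | 194 / 219 | 321 / 386 | 384 / 468 |
| 6 | 386 / 286 | 717 / 829 | 321 / 433 | 210 / 243 | 362 / 448 | 437 / 549 |
| 7 | 355 / 255 | 780 / 930 | 384 / 534 | 228 / 272 | 410 / 525 | 500 / 650 |

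In the most favourable cell (April start, c = 7), reaching 768 still needs 768 − 650 = 118 of the 280 earlier non-completers (42%).

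If the 396 are instead everyone enrolled by the pull (c = 0), the total by closing is 396 × 699/568 = 487 or 396 × 599/468 = 507. That is below 768 at any response rate. No completer figure is projected on this reading, because 29.3% would then count people not yet due as permanently lost.

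**Detectable effect.** With equal arms, 80% power and two-sided 5%, it is 2.802 × √(4(1 − R²)/n) in SD units. Section D.3 adjusts for baseline score and other covariates; the R² values here are assumed, as the plan gives none.

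| n | R² = 0.25 | R² = 0.50 |
|---|---|---|
| 768 | 0.18 | 0.14 |
| 650 | 0.19 | 0.16 |
| 525 | 0.21 | 0.17 |
| 275 | 0.29 | 0.24 |
| 195 | 0.35 | 0.28 |

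The ratio to the value at 768 does not depend on R²: √(768/525) = 1.2, √(768/275) = 1.7, √(768/195) = 2.0.

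**The case against.** Interim counts do not contradict a target, and the plan does not ignore non-response. It has response-rate monitoring (D.1), the Franklin procedure (C.2), the option of more sites (C.1) and an attrition check (D.2). All of this stands. What is missing is an expected yield from these measures, or a sample size that reflects them.

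The 29.3% is a weak guide to the future. The Franklin procedure was due to start in May 2024, under three months before the pull, at the site with most participants. The rate therefore mostly predates it and may understate later response. The 90% scenario allows for this, but 90% is an assumption, and C.2 says only that many Franklin participants join the release programme on which the procedure relies.

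The pace is also assumed. Cohorts are rolling and follow demand (C.1), so accrual could speed up. The enrolment close is inferred from the end of baseline collection, although post-surveys ending six weeks later and follow-up ending six months later fit that inference. The upper boxes of Figure A.3 are not in the text available to this review and may give enrolment totals. The plan should therefore not be faulted for leaving the 396 unexplained.

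A reader might infer that the study will finish with about 145 completers, by applying 29.3% to everyone enrolled. The documents do not support that, for the reason given under the c = 0 reading. Section D.1 also computes response among those eligible to respond by that time point, which points away from that reading.

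**Conclusion.** The point holds as a gap between a stated sample size and what the plan's own counts and dates appear able to deliver. On the 5-to-7-month reading, projected completers are about 195 to 275 at observed response, about 320 to 525 with Franklin at an assumed 90%, and at most about 650 if everyone still to come responds. The last figure leaves aside late returns, faster accrual and added sites. These are survey completers; missing baseline surveys and unanswered items will reduce the analytic sample further. The projections rest on constant pace and an inferred enrolment close; the need for 652 more completers, at least 372 of them from outside the 396, rests on neither.

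Two stronger readings should be resisted. One is that 768 is impossible or contradicted: very unlikely is as far as the documents go, since recovered non-completers, faster accrual or new sites could add to the total. The other is that the study can detect only about 0.34 to 0.40 SD. Those are unadjusted values at 195 to 275, whereas the planned model adjusts for baseline. With the assumed R-squared of 0.25 to 0.50, the range at that size is 0.24 to 0.35 SD, against 0.14 to 0.18 at 768.

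**What to change.** - Keep 768 as the target and state its basis: significance level, power, effect size and any attrition allowance.
- Beside it, give the sponsor's own projected analytic sample, built from actual enrolment to date, the remaining enrolment window, and follow-up response before and after the Franklin procedure, less the loss from baseline and item non-response.
- Give the detectable effect of the covariate-adjusted model at both sizes, with the assumed R-squared.
- State that the primary comparison will be interpreted against the projected or achieved sample, not against 768.
- Optionally, add a sentence that a non-significant difference will not be read as equal effectiveness of the two formats. The plan proposes no such claim, so this is a safeguard and not a correction.

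The cost is a less favourable stated figure. No extra enrolment, data collection or change of model is needed.
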